## 463     14. Additional Tabulations and Analyses

### 464     14.1 Device Issues

465     All reported device issues will be tabulated regardless of whether they were associated with  
466     adverse events. Separate listings will be provided for pre-randomization events and for events  
467     occurring during each treatment arm. For each device issue, the following information will be  
468     listed:

- 469             • Onset date
- 470             • Type of device issue
- 471             • Description of the device issue

### 472     14.2 Amount of CGM and Auto Mode Use

473     Mean  $\pm$  SD or summary statistics appropriate to the distribution will be tabulated for the  
474     percentage of time using the auto mode feature (over the entire period and with the CL system  
475     active) and the CGM for each treatment arm. All CL system discontinuations will be listed in a  
476     table by treatment arm.

477     The percentage of time using the CGM will be calculated by dividing the total number of  
478     available CGM readings by the maximum possible number of readings based on the length of the  
479     study period described in section 4.1.

480     The percentage of time using auto mode over the entire study period will be computed by  
481     summing the gaps in between segments when auto mode is active and dividing by the total  
482     length of the period as defined in section 4.1. For a particular segment, if auto mode is active at  
483     the start of the segment, then the gap will be included in the numerator. However, if it is only  
484     active at the end of the segment, the gap will not be included in the numerator. Gaps greater than

485 90 minutes long where auto mode is active at the start and end of the gap will not be counted in  
486 the numerator because it is possible that the system may not have been on during those periods.

487 Additionally, the percentage of time using auto mode while using the CL system will be  
488 calculated. In these calculations, the numerator will be calculated analogously as described  
489 above. However, the denominator will be the sum of the gaps in between all segments (not the  
490 total possible amount of minutes in the entire period).

491 For example, suppose the CL system provides the following sequence: Auto Mode Active  
492 [0:00:00], Auto Mode Active [0:05:00], Auto Mode Active [0:10:00], Auto Mode Inactive  
493 [0:14:00], Auto Mode Active [0:25:00], Auto Mode Active [0:30:00]}. In this case, the  
494 denominator in the calculation is 30 minutes. During this time, auto mode was inactive from  
495 0:14:00 to 0:25:00, and it was active for the other 19 minutes. Therefore, the percentage of time  
496 using auto mode while using the CL system would be  $100 * (19/30) = 63\%$ .

497 The percentages of time using CGM and the time auto mode is active (over the entire period and  
498 while using the CL system) will be compared between treatments using the same model  
499 described above for the primary outcome.

500 Monthly values for CGM use and auto mode use (over the entire period and while using the CL  
501 system) will also be calculated, and summary statistics will be reported for each of the three  
502 months. The three months will be defined as in section 6.2.3. Within each month, CGM use and  
503 auto mode use will be calculated analogously as described above. Treatment arm comparisons  
504 will not be done for CGM use and auto mode use for any of the three months.

505 Scatter plots of CGM use and auto mode use by time in range (70-180 mg/dL), time  $> 180$   
506 mg/dL, and time  $< 54$  mg/dL will be produced. Summary statistics for these metrics will also be  
507 reported by CGM use and auto mode use.

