189 **5.1 Analysis Cohorts**

- 190 • All analyses will be performed on an intention-to-treat basis with each period included in  
191 the treatment arm assigned by randomization regardless of the actual treatment received.

192        The primary and secondary efficacy analyses for this study will include all randomized  
193        subjects with at least 72 hours of CGM data in either period.  
194        • All subjects with at least 72 hours of insulin data in either period will be included in  
195        insulin analyses.  
196        • A per-protocol analysis for the co-primary outcomes will be conducted by limiting to  
197        subjects who used the CGM at least 80% of the time in both periods and who used auto  
198        mode for at least 80% of the time in each treatment period, unless the sample size for the  
199        analysis is at least 95% of the sample size in the primary analysis.  
200        • All participants will be included in safety analyses, regardless of whether the study was  
201        completed.

202        **6. Analysis of the Primary Efficacy Endpoints**

203        **6.1 Missing Data**

204        Missing data will not be imputed for the primary analysis in this study.

205        **6.2 Statistical Methods**

206        For each co-primary outcome, mean  $\pm$  SD or summary statistics appropriate to the distribution  
207        will be reported by treatment period. A repeated measures least squares regression model with an  
208        unstructured covariance structure will be fit for the two co-primary outcomes. Each of these  
209        models will adjust for period, pre-study 670G system use, and HbA1c at randomization as fixed  
210        effects. The models will include 3 time points: (1) baseline, (2) period 1 outcome, and (3) period  
211        2 outcome. Prior 670G system use in auto-mode at the time of enrollment and HbA1c at  
212        randomization will be included as covariates in the model because they will be used to stratify  
213        randomization.

214        A separate model also will be built for each co-primary outcome with the inclusion of a period  
215        by treatment interaction term to assess for the presence of a carryover effect.

216        All covariates obtained on a continuous scale will be entered into the models as continuous  
217        variables, unless it is determined that a variable does not have a linear relationship with the  

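### The 90-minute gap rule in SAP 14.2 misses long gaps that start in auto mode and end inactive, and leaves excluded gaps in the CL-system denominator; both can distort reported auto-mode use

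*SAP*

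**What the plan says.** SAP 14.2 defines two percentages of auto-mode use. The entire-period metric is computed by "summing the gaps in between segments when auto mode is active and dividing by the total" length of the study period. The CL-system metric uses the same numerator over a different denominator; the sentence reads "above. However, the denominator will be the sum of the gaps in between all segments (not the" and goes on to rule out the full period length as divisor.

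The shared numerator depends on the state at the start of each gap. If auto mode is active at "the start of the segment, then the gap will be included in the numerator. However, if it is only" active at the end, the gap is left out. There is one length limit: gaps greater than "90 minutes long where auto mode is active at the start and end of the gap will not be counted in" the numerator. The reason given is that they are kept out of "the numerator because it is possible that the system may not have been on during those periods".

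Both percentages are compared between treatments with the primary-outcome model. SAP 5.1 also requires, for the per-protocol analysis of the co-primary outcomes, auto "mode for at least 80% of the time in each treatment period, unless the sample size for the" analysis reaches 95% of the primary sample size. Neither SAP 5.1 nor Protocol 10.5 says which of the two percentages the 80% refers to.

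**The concern.** The limit depends on the state at the end of the gap, but its reason does not. If nothing is recorded for several hours, the system may have been off whether it came back in auto mode or out of it. A gap that ends inactive is, if anything, weaker evidence that auto mode ran throughout, yet it is the one credited in full.

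The second issue concerns the CL-system metric alone. Time is taken out of the numerator because the system may have been off, and is then kept in the denominator as time when the system was in use. That does not fit a measure meant to describe use of auto mode while the system was running.

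The two issues push in opposite directions. At stake are the description of adherence, the treatment comparison of auto-mode use, and possibly who falls inside the per-protocol set.

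**Working it through.** **Inputs from the documents.** The counting rules are in SAP 14.2. The maximum period is 2,016 hours, or 84 days (SAP 4.1). The cut is 80% (SAP 5.1).

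**Assumptions.** The documents give no number, length or end state of gaps over 90 minutes. The illustrations assume 85% auto mode in logged time, with logging otherwise complete.

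**1. The SAP's own example.** The "denominator in the calculation is 30 minutes. During this time, auto mode was inactive from" 0:14 to 0:25. Active time is 14 + 5 = 19 minutes, and 19/30 = 63.3%, stated as 63%. The figure is reproduced. The 19 minutes include the gap from 0:10 to 0:14, which starts active and ends inactive, so crediting such gaps is what the rule does. The longest gap is 11 minutes, so the example never exercises the 90-minute limit.

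**2. One day, 5-minute records, one 8-hour gap, all records active except where stated.**
- Gap active at both ends: as written, 960/1,440 = 66.7% on both metrics. If the gap also leaves the CL-system denominator, that metric is 960/960 = 100%; the entire-period value stays at 66.7%.
- First record after the gap inactive: as written, 1,435/1,440 = 99.7% on both metrics. With the limit applied, the entire-period value is 955/1,440 = 66.3% and the CL-system value is 955/960 = 99.5%.

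**3. An 84-day period with one 5-day gap.** Logged time is 84 − 5 = 79 days; logged auto mode is 0.85 × 79 = 67.15 days.
- Gap ends inactive, entire-period: (67.15 + 5)/84 = 85.9% as written; 67.15/84 = 79.9% with the limit applied.
- Gap ends inactive, CL-system: 85.9% as written; 67.15/79 = 85.0% with the gap removed from both parts. The shift is 0.9 points.
- Gap active at both ends, entire-period: 67.15/84 = 79.9% either way.
- Gap active at both ends, CL-system: 67.15/84 = 79.9% as written; 67.15/79 = 85.0% with the gap removed from the denominator.

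**4. Range.** The entire-period value is overstated by exactly the share of the period spent in long active-to-inactive gaps. At 2% it reads 0.85 × 0.98 + 0.02 = 85.3% instead of 83.3%; at 5% it reads 85.8% instead of 80.8%. For the CL-system metric, long gaps active at both ends that fill 2%, 5% or 10% of the period give 83.3%, 80.8% or 76.5% instead of 85.0%. With no gaps over 90 minutes, nothing changes.

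**5. Distance to the 80% cut, entire-period metric.** The cut is 0.80 × 2,016 = 1,612.8 hours. Lifting a participant from 79% to 80% takes 0.01 × 2,016 = 20.2 hours of long active-to-inactive gaps, or 20.2/12 = 1.7 hours a week. From 78% it takes 40.3 hours, from 75% 100.8 hours, and from 70% 201.6 hours.

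**6. Whether the per-protocol analysis is run.** With 100 participants in the primary analysis, five exclusions leave 95% and it is skipped; six leave 94% and it is run. With 112, five leave 107/112 = 95.5% and six leave 106/112 = 94.6%. A few reclassified participants could decide this.

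**The case against.** The strongest reply is that the stakes are low and the effect is unquantified. The co-primary analyses are intention-to-treat and do not use these percentages. The per-protocol analysis is supplementary and may be skipped. Auto-mode use is not a listed primary or secondary endpoint. All of this stands.

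The 5-day gap is also close to the length needed to cross the cut. At 85% use, the value in logged auto mode over 84 days drops below 80% only if the gap exceeds 84 − 84 × 0.80/0.85 = 4.94 days. A 4-day gap gives 0.85 × 80/84 = 81.0% and a 3-day gap 82.0%. The example shows the mechanism, not a typical participant.

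On the denominator, one can argue that the SAP says only that the system may have been off, so counting the time as non-use is cautious. That is a defensible choice for the entire-period metric, where unrecorded time is non-use by definition. It fits poorly with a metric restricted to time on the system, and the caution is not carried through, since gaps that end inactive are credited in full.

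A reader might infer that either issue can move a participant across 80%. On a single metric that does not follow. The denominator issue cannot touch the entire-period metric, and in the example above the gap ending inactive moves the CL-system metric by only 0.9 points. A reader might also infer bias between arms from Protocol Table 4, where the two pumps leave auto mode under different conditions. Table 4 describes auto-mode exits, not missing records. The same rule is applied to both arms and each participant is assigned both pumps, so the comparison is biased only if gap patterns differ by pump, which the documents do not show.

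**Conclusion.** The point holds as a defect in the definition, of minor severity. As written, the numerator rule can overstate entire-period use: 85.9% instead of 79.9% under the assumed 84 days, 85% logged use and one 5-day gap, with about 20 hours of such gaps over 12 weeks enough to lift 79% to 80%. The denominator rule can understate the CL-system metric only: 79.9% instead of 85.0% under the same assumptions.

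The numerator rule can affect the 80% per-protocol cut on the entire-period metric. The denominator rule can do so only if the cut uses the CL-system metric, which SAP 5.1 leaves open. The documents do not support the conclusion that the adherence comparison or the per-protocol set is wrong, because the size depends on the number, length and end state of long gaps. The intention-to-treat co-primary analyses are unaffected.

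**What to change.** In SAP 14.2:
- Apply the 90-minute limit to every gap that starts in auto mode, whatever the state at its end.
- Remove those same excluded gaps from the CL-system denominator. Leave gaps that start inactive in place: the SAP's own example has an 11-minute inactive stretch with no records inside it, so a long gap of that kind may be real manual-mode time.
- Leave the entire-period denominator as it is.
- Add a worked example with a gap over 90 minutes.

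In SAP 5.1, state that the 80% cut uses the entire-period metric, which fits its wording about time in each treatment period.

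The cost is a few sentences and a small program change, with no new data.

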### 508 **14.3 Analysis of Quality of Life Data**

509 Each of the following questionnaires will be administered to all participants who are adults or  
510 adolescents at baseline and at the end of each period:

- 511 • Diabetes Distress Scale
  - 512 ○ Emotional Burden Subscale
  - 513 ○ Physician Related Distress Subscale
  - 514 ○ Regimen Related Distress Subscale
  - 515 ○ Interpersonal Distress Subscale
- 516 • Glucose Monitoring Satisfaction Survey
  - 517 ○ Openness Subscale
  - 518 ○ Emotional Burden Subscale
  - 519 ○ Behavioral Burden Subscale
  - 520 ○ Trust Subscale
- 521 • Hypoglycemia Confidence Survey
- 522 • Diabetes Technology Attitudes Survey
- 523 • INSPIRE Survey (separate versions for adolescents and adults)

524 The electronic data capture system for this study will not allow the subject to submit any  
525 questionnaires until all items are completed. However, it is still possible to have missing data,  
526 because each question will provide participants with the option to not answer. Analysis will be  
527 limited to subjects who submit a questionnaire (no imputation).

528 For each full questionnaire and subscales, total scores (or mean scores depending on the scoring  
529 instructions for the survey) will be calculated and summary statistics appropriate to the  
530 distribution will be tabulated at each time point by treatment arm. For questionnaires and  
531 subscales where the total score is calculated, only subjects completing the entire survey (or entire  
532 subscale) will be included in the tabulations of summary statistics. Since it is possible for a  
533 subject to complete all questions in a particular subscale but not in the whole survey, it is  
534 possible that the N will differ between the full questionnaire and the subscales. The distribution  
535 of responses for each individual question at each time point will also be tabulated. Total scores  
536 for the full questionnaires and subscales will also be compared between treatments using the  
537 same model described above for the primary outcome.

#### 538 **14.4 Pump Settings**

539 The relationship between the following pump settings and time in range (70-180 mg/dL), time >  
540 180 mg/dL and time < 54 mg/dL will be examined:

- 541 1) Active Insulin Time (AIT)
- 542 2) Set point
- 543 3) Insulin-Carbohydrate Ratio (ICR)

544 A participant should have a value of Insulin-Carbohydrate Ratio (ICR) for each auto-bolus  
545 delivered. The average of all values will be calculated for each participant by period. An  
546 average of Active Insulin Time will be calculated for each participant and will be weighted by  
547 the amount of time spent at each value. Mean  $\pm$  SD or summary statistics appropriate to the  
548 distribution will be reported for these metrics by treatment group. Summary statistics for the  
549 CGM metrics will be reported by treatment group for categories of AIT and ICR.

550 Set point is the daily sensor glucose target while in auto mode. The only two possible values are  
551 100 mg/dL and 120 mg/dL. The percentage of time a participant has spent with a set point of  
552 100 mg/dL will be calculated for each participant. Scatter plots of percent time with a set point  
553 of 100 mg/dL and time in range, time above 180 mg/dL and time below 54 mg/dL will be shown.

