1007          not completed in-person. Participants requiring a remote final visit will be transitioned off of the  
1008          study device during the remote contact and an arrangement will be made between site staff and  
1009          the participant to return all required study devices either in-person or via mail.

1010          **5.1.5.3 Setpoint adjustments during 670G 4.0 AHCL use**

1011          All participants in the 670G 4.0 AHCL arm will start with an auto mode target glucose set point  
1012          of 120 mg/dL (6.7 mmol/L). At the auto mode initiation contact, participants will be reminded to  
1013          obtain an overnight fingerstick blood glucose measurement (between 2-3AM) for 2-3 nights  
1014          following auto mode initiation and if SMBG is <70 mg/dL to treat with carbohydrate,  
1015          discontinue closed loop mode, and notify the investigator or designee the next day for advice.  
1016          Study staff will inquire about the fingersticks and reinforce the importance of these fingersticks  
1017          at both the 24-hour and 3-7 day follow-up phone calls. At the 2-week assessment visit the target  
1018          glucose set point should be lowered to 100 mg/dL (5.6 mmol/L) if the participant meets the  
1019          criteria listed below since the previously scheduled visit or contact and the site investigators have  
1020          no other clinical reason not to reduce the setpoint:

1022           • No severe hypoglycemia; AND

1023           ○ No more than 1% of sensor glucose readings <54 mg/dL (3.0 mmol/L) for the  
1024            24-hour time period based on review of CGM download AND no sensor  
1025            glucose readings less than 54 mg/dL from Midnight to 6AM; OR  
1026           ○ No more than 3% of sensor glucose readings less than 70 mg/dL (3.9 mmol/L)  
1027            for 24 hours

1028  
1029       If the participant does not meet these criteria the setpoint should remain at 120 mg/dL (6.7  
1030       mmol/L) and the participant should be reevaluated at 4, 6, and 9 weeks to see if the setpoint can  
1031       be reduced to 100 mg/dL (5.6 mmol/L) using the same criteria. When the setpoint is lowered,  
1032       the same requirement as above will be provided regarding overnight fingersticks.

1033       The setpoint may be adjusted at any time if clinically appropriate per investigator's opinion.

1034  
1035       **5.1.6 Device Data Uploads During the Crossover Trial**

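### The set-point scatter plots in SAP 14.4 are confounded by the rule that assigns the set point, and can show less hypoglycemia with more time at 100 mg/dL even if that setting increases it

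*SAP*

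**What the plan says.** **How the set point is assigned (Protocol 5.1.5.3).** "All participants in the 670G 4.0 AHCL arm will start with an auto mode target glucose set point" of 120 mg/dL. At the 2-week visit the target "glucose set point should be lowered to 100 mg/dL (5.6 mmol/L) if the participant meets the" criteria and the site has no other clinical reason against it. The criteria are no severe hypoglycemia and either of two branches:

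- "No more than 1% of sensor glucose readings <54 mg/dL (3.0 mmol/L) for the" full day, with no reading <54 mg/dL between midnight and 6AM; or
- at most 3% of readings <70 mg/dL over 24 hours.

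The data judged are those since the previous scheduled visit or contact. Anyone who does not qualify stays at 120 mg/dL, and "the participant should be reevaluated at 4, 6, and 9 weeks to see if the setpoint can" be reduced under the same criteria. The investigator may also change the set point at any time.

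**How the set point is analyzed (SAP 14.4).** Each participant gets one value, the percentage of time at the lower target, and scatter plots of the percentage of time at a set point "of 100 mg/dL and time in range, time above 180 mg/dL and time below 54 mg/dL will be shown". I read this as the AHCL period, because Protocol Table 4 gives the 670G 3.0 only the 120 mg/dL target. Protocol 10.4 computes CGM indices over the first 84 days after auto mode starts. SAP 14.4 makes no split at the switch, no within-participant comparison, no adjustment for earlier hypoglycemia, and gives no caution. SAP 12 does give one for subgroup analyses.

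**The concern.** The plot is meant to show how the set point relates to hypoglycemia. Under the rule, hypoglycemia also decides the set point. People prone to low glucose are lowered later or not at all, and the readings that kept them at 120 mg/dL are counted in the outcome. Both features push the plotted association in the negative direction.

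The 100 mg/dL target exists only on the investigational pump, and SAP 14.4 is the only set-point-specific analysis planned. A plot in which more time at 100 mg/dL goes with less time <54 mg/dL could be taken as reassurance about that setting, and the design cannot support that reading.

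**Working it through.** SAP 14.4 states no figure to reproduce. The check is a simulation of the planned plot under a known true effect.

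**Inputs from the documents.** 100 completers (Protocol 10.3); 84 days per period; start at 120 mg/dL; decisions at weeks 2, 4, 6 and 9 with both branches joined by OR. Between-person spread is guided by the adolescent study-phase daytime table in Protocol 1.1.4: 2.7 ± 1.30% at ≤3.8 mmol/L, 1.1 ± 0.82% at ≤3.3 and 0.4 ± 0.41% at ≤2.7.

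**Assumptions.** Time <70: mean 2.75%, SD 1.4. Time <54 is not tabulated, so mean 0.65% and SD 0.6 were interpolated. Both are lognormal, with correlation 0.8 on the log scale. The log-SD of a 14-day window is 0.5. Night readings <54 come in episodes of about 4.

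**Why the rule selects.** At week 2 the decision window runs from about day 5 to day 14, which is 9 nights. With readings every 5 minutes (assumed), midnight to 6AM holds 6 × 12 = 72 readings, so 72 × 9 = 648 in the window. If the night rate equals the 24-hour rate p, the chance of no night reading <54 is exp(−648p/4):

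- p = 0.30%: exp(−0.486) = 0.62
- p = 0.65%: exp(−1.053) = 0.35
- p = 1.00%: exp(−1.62) = 0.20, and above 1% the first branch fails outright.

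For the second branch, the log-variance is ln(1 + (1.4/2.75)²) = 0.230, so the log-SD is 0.480 and the log-mean is ln 2.75 − 0.115 = 0.896. The share of people whose long-run time <70 is at most 3% is Φ((ln 3 − 0.896)/0.480) = Φ(0.42) = 0.66. The remaining third depend on the first branch or on a favorable window.

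**Result of the planned plot.** Mean Spearman correlation of percent time at 100 mg/dL with period time <54, by the true multiplier of the 100 mg/dL setting on time <54 (— = no value available):

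| Scenario | ×1 | ×1.5 | ×2 | ×3 |
|---|---|---|---|---|
| Rule followed, base case | -0.58 | -0.50 | -0.43 | -0.30 |
| Rule followed, returned to 120 after failing the limits | -0.73 | — | -0.65 | -0.57 |
| <54 and <70 less correlated (0.3), window log-SD 0.3 | -0.38 | -0.27 | -0.19 | -0.06 |
| Homogeneous population (SD of <54 = 0.2, of <70 = 0.6) | -0.45 | -0.28 | -0.14 | +0.04 |
| Half of decisions follow the rule | -0.28 | — | -0.17 | -0.09 |
| A quarter follow the rule | -0.14 | -0.08 | -0.02 | +0.05 |
| Homogeneous and half follow the rule | -0.22 | -0.07 | +0.06 | +0.18 |
| Set point unrelated to hypoglycemia | 0.00 | +0.08 | +0.12 | +0.18 |

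In the base case the correlation was negative in every simulated trial. Participants with more than 60% of time at 100 mg/dL had 0.48 to 0.99 percentage points less time <54 than the rest, across multipliers from 1 to 3. With little hypoglycemia (mean <54 of 0.2%, <70 of 1.5%), about 1% were never lowered. In some of those trials every participant had the same horizontal value and the correlation was undefined.

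**Result of a within-participant contrast.** Mean time <54 while at 100 minus while at 120 mg/dL, in base-case participants with time at both: +0.07, +0.20, +0.34, +0.60 and +1.14 points for multipliers of 1, 1.25, 1.5, 2 and 3. The sign is right. The +0.07 under no effect is regression to the mean, because people are lowered after a good window. Set against the +0.20 seen at a 25% increase, it is 0.07/0.20, about a third.

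**The case against.** The best defense is that little depends on these plots. They sit under additional tabulations, carry no test or p-value, belong to none of the multiplicity families in SAP 13, and feed no co-primary, secondary or safety conclusion. The randomized comparison of time <54 evaluates AHCL with its set-point strategy included. It is repeated without the first four weeks (SAP 4.1.1), after the week-2 decision and usually the week-4 decision, and is shown by month and arm (SAP 6.2.3). All of this stands, and it limits the point to interpretation of a descriptive display.

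Second, the rule is looser than a bar on anyone with hypoglycemia. Someone with night readings <54 can still qualify through the <70 branch, there are three rechecks, and the investigator may act at any time. This also stands, and the table shows how far decisions unrelated to the limits dilute the bias. The simulation treats discretion as blind to low glucose. Discretion that itself responds to hypoglycemia would dilute it less.

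Third, the within-participant contrast has its own faults: regression to the mean in the opposite direction, and mixing with time since auto mode started. Leaving out the decision window leaves only about 5 days at 120 mg/dL for those lowered at week 2. These faults argue for adding the contrast with stated limits. They do not support leaving the plots unlabeled.

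**Conclusion.** The point holds as a bias in a descriptive analysis. With the rule followed and spread close to the protocol's own tables, the plot shows a correlation of about -0.6 under no effect and about -0.4 when the setting doubles time <54. It can therefore point the wrong way. The size rests on an interpolated distribution for time <54, assumed window variability, and the share of decisions that follow the limits. The documents fix none of these.

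A reader might infer that the plot will make 100 mg/dL look safer whatever its true effect. The documents do not support that: where discretion unrelated to hypoglycemia dominates, or a large effect meets a homogeneous population, the association vanishes or turns positive. Where hypoglycemia is rare, the plot may simply be uninformative. A reader might also infer that the trial's hypoglycemia conclusion is compromised. It is not, because the randomized co-primary comparison does not use this plot. The bias was quantified only for time <54, not for time in range or time >180.

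**What to change.** In SAP 14.4:

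1. Add a descriptive within-participant comparison, in the AHCL period, of time <54, time in range and time >180 mg/dL while the set point was 120 versus while it was 100 mg/dL.
2. List participants who were never lowered separately, with their CGM metrics.
3. Keep the across-participant set-point plots if wanted, but state beside them that Protocol 5.1.5.3 assigns the set point partly from low-glucose readings in the same period, so the plots do not show the effect of the setting.
4. State the limits of the new contrast: it mixes set point with time since auto mode start and carries slight regression to the mean. A repeat without the decision window is optional.

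The cost is a few lines of SAP text and modest programming, since SAP 14.4 already needs set-point time and CGM data for each participant. No change to the clinical set-point rule is proposed.
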